## **7. Randomization and Blinding**

Participants will be randomized into intervention or sham groups using a computer-generated randomization list ([randomization.com](http://randomization.com)). Allocation will be concealed in sealed opaque envelopes.

Blinding:

- Participants will not be informed of the intervention type (reflexology or sham).
- Therapists will be trained but informed only that they are applying a “foot massage technique,” with no access to study allocation. They will not communicate with each other.
- Outcome assessors and data analysts will remain blinded to group allocation.

## **8. Data Collection and Management**

Data will be collected at baseline and throughout the intervention sessions. Each participant will be assigned an anonymous code. Data will be stored in password-protected electronic files accessible only to the research team.

## **9. Statistical Analysis Plan**

Descriptive statistics (mean  $\pm$  SD) will be used for quantitative variables.

- Primary outcome (BAI): Repeated measures ANOVA (Group  $\times$  Time) with post-hoc Bonferroni.

- Secondary outcomes (POMS): Repeated measures ANOVA (Group × Time).
  - Adverse effects: Frequency distribution and Chi-square tests.
- Significance level:  $p < 0.05$ . SPSS (IBM, v.29) will be used.

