## **2. Objectives**

Primary Objective:

- To evaluate the effect of foot reflexology on anxiety symptoms, measured by the Beck Anxiety Inventory (BAI).

Secondary Objectives:

- To assess changes in psychological well-being and relaxation using the Tension-Anxiety subscale of the Profile of Mood States (POMS, reduced version).
- To record and analyze adverse effects related to the interventions.

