## **3. Study Design**

This is a randomized, parallel, controlled, double-blind clinical trial with two arms:

1. Foot reflexology intervention.
2. Sham reflexology (control group).

The study will last approximately 5 weeks, with 10 intervention sessions per participant.

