## **4. Eligibility Criteria**

Inclusion Criteria:

- Adults aged 18–80 years.
- Clinical diagnosis of anxiety disorder (confirmed by physician or psychologist).
- BAI score  $\geq 11$  (mild anxiety or higher).
- Ability to attend all intervention sessions and assessments.

Exclusion Criteria:

- Current psychiatric or psychological treatment with medication adjustments in the last 30 days.
- Use of other complementary therapies for anxiety during the study period.
- History of severe psychiatric disorders (psychosis, bipolar disorder).
- Foot injuries, ulcers, or contraindications to manual therapy.
- Pregnancy.

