## **6. Outcome Measures**

Primary Outcome:

- Reduction in anxiety symptoms assessed by Beck Anxiety Inventory (BAI).
- Score range: 0 to 63.
- Higher scores indicate worse anxiety.

- Time points: baseline, after session 5, after session 10.

Secondary Outcomes:

- Tension-Anxiety Subscale of the Profile of Mood States (POMS – reduced version).
- Score range: 0 to 36.
- Higher scores indicate worse tension-anxiety.
- Time points: after each of the 10 sessions.
- Adverse effects.
- Recorded during and after each session.
- Frequency and intensity analyzed descriptively.

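### The primary BAI test uses baseline as a level of Time in a 2-df Group × Time ANOVA; it is valid, but usually less precise than adjusting sessions 5 and 10 for baseline BAI

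*Protocol*

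**What the plan says.** Section 9 of the protocol fixes the analysis: "Primary outcome (BAI): Repeated measures ANOVA", specified as Group × Time, "with post-hoc Bonferroni", at a 0.05 level. Section 6 gives the schedule, "Time points: baseline, after session 5, after session 10", and defines the outcome as "Reduction in anxiety symptoms assessed by Beck Anxiety Inventory (BAI"). Section 3 has two arms.

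Section 9 does not list the levels of Time, but the three assessments in section 6 are the only ones it can refer to, so baseline is one of them. Baseline BAI is not named as a covariate anywhere. Every participant has a score at entry, because section 4 requires a BAI of at least 11 ("mild anxiety or higher"). Sections 2, 6 and 9 do not rank session 5 above session 10 or the reverse.

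**The concern.** In a randomised trial the baseline score cannot carry a treatment effect. Its use is to explain variation in the later scores. As a level of Time it is treated instead as one more response, and the interaction compares the arms on departures from a mean that includes it. That is much like analysing change scores, which remove the baseline with a fixed weight of one, whereas a covariate takes the weight that the data support. When baseline and later scores are only moderately correlated, the fixed weight adds noise.

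What is at stake is power and the form of the result. The interaction F is not itself an estimated difference between arms at a visit. The visit and direction of any effect have to be read from the post-hoc comparisons or the means.

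**Working it through.** **Inputs from the protocol.** Arms: 2 (section 3). BAI assessments: 3, including baseline (section 6). Level: 0.05 (section 9). Interaction df = (2 − 1)(3 − 1) = 2. The protocol gives no power figure to reproduce.

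**Assumptions, because the protocol gives none.** n = 30 per arm, SD = 1 at each visit, compound symmetry with correlation ρ = 0.5. The effect size d is set so that ANCOVA at session 10 has 80% power for a full effect there.

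**Formulas (noncentral F, noncentrality λ).**
- ANCOVA at session 10: λ = n·d² / [2(1 − ρ²)], df 1 and 2n − 3 = 57. With d = 0.637, λ = 30 × 0.4058 / 1.5 = 8.12, power 80%.
- Group × Time: λ = (n/2)·Σ(δt − δ̄)² / (1 − ρ), df 2 and 2(2n − 2) = 116, where δt is the arm difference at each of the three times.
- Joint baseline-adjusted test over both visits: λ = (n/2)·δ′S⁻¹δ, df 2 and 2n − 4 = 56. S has 1 − ρ² = 0.75 on the diagonal and ρ − ρ² = 0.25 off it, so S⁻¹ has 1.5 and −0.5.

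**Results at ρ = 0.5** (effects at baseline, session 5, session 10, in units of d; d² = 0.4058):

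| Profile | Interaction λ | Power | Joint adjusted λ | Power |
|---|---|---|---|---|
| Gradual (0, ½, 1) or fading (0, 1, ½) | 15 × 0.5 × 0.4058 / 0.5 = 6.09 | 57.9% | 15 × 1.375 × 0.4058 = 8.37 | 71.4% |
| Full by session 5 (0, 1, 1) | 15 × 0.667 × 0.4058 / 0.5 = 8.12 | 71.3% | 15 × 2 × 0.4058 = 12.17 | 87.0% |
| One visit only (0, 1, 0) or (0, 0, 1) | 8.12 | 71.3% | 15 × 1.5 × 0.4058 = 9.13 | 75.3% |

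Both tests have 2 df and both use both visits, so the gain comes from how baseline is handled and not from picking a favourable visit.

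**Dependence on correlation.** At equal variances, the variance of a change score relative to ANCOVA is 2(1 − ρ)/(1 − ρ²) = 2/(1 + ρ): 1.54 at 0.3, 1.33 at 0.5, 1.18 at 0.7, 1.11 at 0.8. The power gap shrinks in step. Over 20, 30 and 50 per arm and compound symmetry 0.3 to 0.9, joint minus interaction runs from −1.1 to +25.5 points. At 0.9 it is only −1 to +2.

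**Decaying correlation (AR(1), 30 per arm, Greenhouse-Geisser interaction, simulated).** For a gradual effect the joint test is about 1 point lower at adjacent correlation 0.8, and 5 to 6 points lower at 0.9 (about 69% against 74–75%). The other profiles gain in the same settings; for an effect full by session 5 at 0.8, for example, the joint test has 91% against about 85%.

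**Validity.** With 30 per arm and no true effect, the uncorrected interaction F rejected in 4.8% of runs under compound symmetry and 5.9% under AR(1) 0.8.

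**The case against.** Group × Time is a standard analysis for two arms at three times and contradicts nothing else in the protocol. Section 9 also plans an error-controlled follow-up step, and nothing there rules out reporting differences between arms with confidence intervals. All of this stands. A reader might infer that the primary test is invalid; the null simulations do not support that, and the slight excess without sphericity is dealt with by a routine correction that a separate SAP may specify.

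A reader might also infer that session 10 ought to be the sole deciding visit. The protocol does not support that, since it lists both post-baseline visits without ranking them. The figures do not favour it generally either. At compound symmetry 0.5, ANCOVA at session 10 has 80% power against 58% for a gradual effect, but 29% against 58% for a fading one, and 5% against 71% if the effect is at session 5 only. Under AR(1) 0.8 it falls below the planned test for every profile except the gradual one.

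Three narrower objections also hold. The joint test is no more directional than the interaction; its advantage is precision, and direction comes from the adjusted differences reported beside it. It does not win everywhere, as the AR(1) results show. And the wide range that section 4 allows for baseline scores does not prove a loss: the loss depends on correlation, and if a wider spread raised the correlation, the loss would shrink.

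The unseen SAP does not remove the point, because the protocol itself states the primary method and it is that choice which is at issue.

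**Conclusion.** The point holds as one of efficiency, not validity. The planned interaction test usually gives up precision that a score already collected could provide. In the illustration the loss is about 13 points for a gradual or fading effect (71.4 − 57.9 = 13.5), 16 for an effect full by session 5 (87.0 − 71.3 = 15.7) and 4 for an effect at one visit (75.3 − 71.3 = 4.0). These figures show direction and rough size only: sample size, correlation, effect and profile are all assumed. The benefit is negligible at high, even correlation and reverses for a gradually building effect under strongly decaying correlation.

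That no visit is singled out is a question of targeting. A single contrast, at one visit or on the mean of both, would give a sharper primary result, but which one is for the sponsor to decide. The change is worth making, but the planned analysis would not invalidate the trial.

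**What to change.** In section 9, replace the Group × Time test of BAI with a model that has session-5 and session-10 BAI as outcomes and baseline BAI (with its interaction with visit) as covariate. Make the joint 2-df between-group test over both visits the primary test, and report the baseline-adjusted difference between arms with a 95% CI at each visit.

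Optionally, the sponsor may name one deciding contrast instead (session 5, session 10, or their mean) and state it in sections 2, 6 and 9. That choice trades power for some profiles against others, as shown above, and should be made before unblinding.

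The cost is wording. All three BAI scores are already collected, and the SPSS version named in section 9 can fit the model. The price in power is the small or negative return in the high-correlation and strongly decaying settings described above.

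### If Bonferroni is applied across the BAI follow-up comparisons, Holm would give more power at the same family-wise error; the Group × Time test itself is unaffected

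*Protocol*

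**What the plan says.** Protocol section 3 describes a "randomized, parallel, controlled, double-blind clinical trial with two arms". Section 6 makes the BAI the primary outcome and lists three measurements: "Time points: baseline, after session 5, after session 10". No single visit is named as the primary one.

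Section 9 gives the analysis: "Primary outcome (BAI): Repeated measures ANOVA" with the Group × Time factors, "with post-hoc Bonferroni", at the 5% significance level. It does not say which follow-up comparisons are meant, or whether the correction runs across visits. For reporting, it mentions means with SDs and significance tests, and no confidence intervals.

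**The concern.** A significant Group × Time result says that the arms change differently over three measurements. It does not say at which visit they differ. In this plan, the follow-up comparisons carry that information, including whether reflexology and sham differ at the end of treatment.

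Two contrasts compare the arms after treatment has begun: after session 5 and after session 10. If these are corrected together by Bonferroni, each must reach 0.025 whatever the other shows. Holm asks 0.025 of the smaller p-value only. Once that is met, the other is tested at 0.05. Holm needs no further assumptions and has the same family-wise error guarantee. What is at stake is some power on these contrasts. No error rate is breached.

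**Working it through.** **Inputs from the protocol.** Two arms (section 3), two post-baseline BAI visits (section 6), significance level 0.05 (section 9; taken as two-sided, which is not stated). The protocol has no power figure to reproduce.

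**Assumed inputs.** Session-10 contrast: 80% power at 0.05. Session-5 contrast: 80%, 60% or 30%. Correlation between the two test statistics: 0.5 to 0.8. Normal theory. The contrasts are taken on their own, without requiring a significant Group × Time test first.

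**Step 1: Bonferroni over two contrasts.** The critical value moves from 1.960 (p = 0.05) to 2.241 (p = 0.025). The expected test statistic is 1.960 plus the normal quantile of the assumed power, and power at 0.025 is Φ(expected statistic − 2.241):

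- 80% at 0.05: 1.960 + 0.842 = 2.802; Φ(2.802 − 2.241) = Φ(0.561) ≈ 0.71.
- 60% at 0.05: 1.960 + 0.253 = 2.213; Φ(2.213 − 2.241) = Φ(−0.028) ≈ 0.49.

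**Step 2: Holm over the same two contrasts.** Session 10 is rejected if p10 ≤ 0.025, or if 0.025 < p10 ≤ 0.05 and p5 ≤ 0.025. The second term is the gain. It cannot exceed 80 − 71 = 9 points, and it shrinks as session 5 gets weaker. Simulation with 2,000,000 draws of correlated normal statistics gives:

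| Session-5 power at 0.05 | Quantity | Bonferroni | Holm |
|---|---|---|---|
| 80% | session 10 | 71% | about 76% |
| 80% | both visits | 57-63% | 68-71% |
| 60% | session 10 | 71% | 73-74% (gain 1.5-3 points) |
| 60% | session 5 | 49% | about 57% |
| 30% | session 10 | 71% | gain 0.1-0.8 points |

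**Step 3: at least one rejection.** Holm's first step is Bonferroni's threshold, 0.025 for the smaller p-value, so this probability is identical (85.3% for both with equal 80% power and correlation 0.5). Check: P(at least one) + P(both) equals the sum of the two powers. With P(at least one) fixed, the gain in showing both must equal the sum of the two single-contrast gains. At correlation 0.5 each contrast gains about 5.2 points, and 2 × 5.2 = 10.4 agrees with the rise in showing both from about 57% to 68%.

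**Step 4: another set of assumptions.** Take 40 per arm, correlation 0.6 and a standardised effect of 0.5 at session 10. With an effect of 0.25 at session 5, session-10 power goes from 49.8% to 50.6% and session-5 power from 13.2% to 18.5%; at least one rejection stays at 51.5%. With 0.5 at both visits, session-10 power goes from 49.8% to 54.9%. The pattern is the same: the session-10 gain needs a session-5 effect of similar strength, and otherwise most of the gain goes to session 5.

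**Step 5: error rate.** With no effect at either visit and correlation 0.6, the simulated family-wise error for two contrasts is 0.045 under both methods.

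**The case against.** The strongest case against is that nothing here is wrong. Bonferroni is valid and pre-specified, and no other statement in the protocol conflicts with it. This stands, and it limits the point to an improvement.

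Four further objections deserve an answer.

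- **The primary test.** A reader might infer that Bonferroni costs power on the primary analysis. Section 9 does not support that: the Group × Time test is made at 0.05, and the correction belongs to the comparisons after it.
- **Scope of the correction.** Section 9 does not say that the correction runs across visits. Applied separately within each visit, two arms give a single pair, so the between-arm contrasts carry no penalty. A contrast with 80% power would keep it, and Holm across visits would lower it to about 76%, in return for family-wise control over the two visits. The claimed loss therefore holds only under correction across visits.
- **Size of the family.** A reader might count every pair of arm-by-visit cells and infer a much larger loss. The protocol does not say that all pairs will be tested. Such a loss would also come from the size of the family, not from choosing Bonferroni over Holm.
- **Intervals.** Bonferroni has matching simultaneous confidence intervals; Holm has no simple ones. This is a real trade-off. Section 9 mentions no intervals, so as written it is no reason to keep Bonferroni. A separate analysis plan that adds simultaneous intervals could make it one.

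**Conclusion.** The point holds as a minor, inexpensive improvement to the BAI follow-up comparisons, on condition that they are corrected across visits. In that case Holm is never worse than Bonferroni on rejections and keeps the same family-wise error.

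The size is modest. The session-10 gain is about 5 points when both contrasts have 80% power, and it falls to a point or less when session 5 is much weaker, which is plausible halfway through treatment. The clearer gains are in showing both visits and in the weaker session-5 contrast. All percentages rest on assumed power and correlation, because the protocol gives no sample size, SD or effect size.

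**What to change.** In section 9, replace the post-hoc phrase for the BAI with wording such as: *two follow-up between-arm comparisons of BAI, at session 5 and session 10, with Holm adjustment (the smaller p-value against 0.025; if significant, the other against 0.05)*.

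This costs one line and needs no extra participants or data. It also settles which comparisons are corrected and that the correction runs across visits. The small downside is in reporting: ordinary 95% intervals would stand beside Holm-adjusted p-values, and the two can occasionally disagree. If matching simultaneous intervals are wanted, keeping Bonferroni for the same two named contrasts is a defensible alternative.

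### Repeated-measures ANOVA in SPSS, as ordinarily run, drops anyone with one missing score; a mixed model would be a cheap improvement, mainly for the ten-point POMS

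*Protocol*

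**What the plan says.** Protocol Section 9 names one method for both scales. For the primary outcome it reads "Primary outcome (BAI): Repeated measures ANOVA (Group" × Time), "with post-hoc Bonferroni". For the secondary outcome it reads "Secondary outcomes (POMS): Repeated measures ANOVA (Group × Time"). It adds "SPSS (IBM, v.29) will be used".

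Section 6 sets the number of repeated scores. For the BAI it gives "Time points: baseline, after session 5, after session 10", and for POMS "Time points: after each of the 10 sessions". Section 3 states "The study will last approximately 5 weeks, with 10 intervention sessions per participant", and Section 8 states "Data will be collected at baseline and throughout the intervention sessions".

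A qualifying BAI score is an entry criterion in Section 4, so the baseline BAI is always present and only two BAI scores can go missing. Section 4 also requires participants to be able to attend all sessions and assessments. The Protocol gives no expected rate of missed sessions or dropout.

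**The concern.** The usual SPSS repeated-measures ANOVA takes one row per participant and deletes any row with a gap. One missing POMS form therefore discards the participant's other nine scores. A missing session-5 BAI removes someone who has both baseline and session-10 scores.

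Ten consecutive forms per participant make POMS the more exposed scale. At stake are precision already paid for in collected data and, for the BAI under one particular pattern of missingness, bias. A likelihood-based mixed model uses the scores that exist. Because Section 9 commits to the method and the software, this is a comment on a choice the Protocol makes, not on detail it leaves open.

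**Working it through.** There is no figure in the Protocol to reproduce: it states no sample size, SD, effect size or missing rate. Every missing rate and correlation below is an assumption.

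**Inputs.** From Section 6: k = 10 POMS scores and 3 BAI scores. From Section 4: BAI baseline always present, so k = 2 BAI scores at risk. Assumed: share of scores missing p = 2%, 5% or 10%.

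**Share of participants excluded by listwise deletion**

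- Independent misses: 1 − (1 − p)^k. POMS at 5%: 1 − 0.95^10 = 0.401.
- Dropout at a constant hazard h per assessment, with h set so that the overall share missing is p; excluded = 1 − (1 − h)^k. POMS at 5%: h = 0.00935, so 1 − 0.99065^10 = 0.090.
- Clustered misses: beta-binomial with intra-participant correlation 0.3 (assumed), so a + b = 1/0.3 − 1 = 2.333 and b = (1 − p) × 2.333. Excluded = 1 − Π(b + i)/(a + b + i), i = 0 to 9. POMS at 5%: 0.197.

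| Share missing | POMS dropout | POMS clustered | POMS independent | BAI dropout | BAI independent |
|---|---|---|---|---|---|
| 2% | 4% | 8% | 18% | 3% | 4% |
| 5% | 9% | 20% | 40% | 7% | 10% |
| 10% | 18% | 36% | 65% | 13% | 19% |

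**POMS precision.** The table gives the complete-case SE divided by the mixed-model SE, with the covariance taken as known. The contrasts are the last session, the mean of ten sessions, and session 10 minus session 1. The correlation structures are AR(1) 0.5, 0.7 and 0.9 and exchangeable 0.6.

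| Share missing | Dropout | Clustered | Independent |
|---|---|---|---|
| 2% | 1.00–1.02 | 1.03–1.04 | 1.09–1.11 |
| 5% | 1.00–1.04 | 1.08–1.12 | 1.26–1.30 |
| 10% | 1.00–1.08 | 1.18–1.24 | about 1.6–1.7 |

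The equivalent loss of participants is 1 − 1/ratio². At 5% this is 0–8% under dropout (1 − 1/1.04² = 0.075), 14–20% under clustered misses, and 37–41% under independent misses.

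Cross-check: under exchangeable correlation 0.6 with 5% independent misses, the mixed model keeps 99.6% of the information on a constant group difference, while listwise deletion keeps 59.9% of participants. √(0.996/0.599) = 1.29, inside the range above.

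**BAI precision.** For the session-10 group difference, with both analyses adjusted for baseline and equal or AR(1) correlations of 0.5 and 0.7, the SE ratio is 1.00–1.01 under dropout. Under independent misses it is 1.01, 1.03 and 1.06–1.07 at 2%, 5% and 10% missing.

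**BAI bias.** This was simulated with no true effect, 10% or 20% of session-10 scores missing in each arm, and an odds ratio of 2 or 4 per SD of baseline-to-session-5 change.

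- Mechanism in one arm only: 0.02–0.17 SD for the complete-case change; at most 0.003 SD for the mixed model with baseline as a third response.
- Same mechanism in both arms: at most 0.004 SD for every method.

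The mixed model does well here because the simulated scores are missing at random.

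**Choice of POMS fallback covariance.** Suppose the truth is exchangeable 0.6 and an AR(1) model with lag-one correlation 0.6 is used.

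- Mean of ten sessions: true variance 0.6 + 0.4/10 = 0.640; AR(1) variance (1/10)[1 + 2Σ(1 − k/10)0.6^k] = 0.325. The critical value becomes 1.96 × √(0.325/0.640) = 1.40, so a nominal 5% test rejects about 16% of the time.
- Session 10 minus session 1: true variance 2(1 − 0.6) = 0.80; AR(1) variance 2(1 − 0.6^9) = 1.98. The test rejects about 0.2% of the time.

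AR(1) alone is therefore a poor fallback.

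**The case against.** The strongest reply is that the loss comes from missing-data handling, which Section 9 does not fix. ANOVA on imputed scores would satisfy its wording, and a statistical analysis plan not shown here could provide for imputation. A reader might infer that the Protocol prescribes a complete-case analysis; it does not. This stands, and it confines the point to what the named procedure does as ordinarily run. It does not remove the point, since the method itself is fixed.

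Second, misses may be few. Section 4 asks for ability to attend, POMS is indexed by session and not by date, and a postponed session leaves no gap. Scores are collected around sessions, so a missing form will mostly mean a missed session, and such gaps tend to cluster or to be dropout. A reader might infer from the 40% figure that POMS will lose that share of participants. The Protocol gives no rate, and independent misses are the worst of the patterns considered.

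Third, the effect on the primary outcome is small. A reader might infer that the BAI result will be biased. That needs missingness to depend on early change differently in the two arms, and nothing in the Protocol points to this.

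Fourth, the SE ratios are for single contrasts, not for the nine-degree-of-freedom POMS interaction, for which no power loss was computed. Nor was the heterogeneous Toeplitz model tested with estimated covariance: the one such check fitted AR(1), with 30 per arm assumed, and gave similar ratios. Both limits stand.

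**Conclusion.** The point holds as a cheap improvement, mainly for the secondary outcome. At an assumed 5% of POMS forms missing, the precision cost runs from nothing, if sessions are rebooked, and almost nothing under dropout, to the equivalent of 14–20% of participants under clustered misses. The 37–41% under independent misses is an upper bound. For the BAI the gain is a few per cent in standard error at most, plus protection against a differential mechanism that is possible but not indicated. All of this rests on assumed missing rates, an assumed clustering correlation of 0.3 and assumed correlations between scores. It should be changed, but it does not undermine the trial. Confidence is moderate.

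**What to change.** In Section 9, replace repeated-measures ANOVA with a linear mixed model for repeated measures (SPSS MIXED, REML, Kenward-Roger degrees of freedom), with participants in their randomised group, and keep the Group × Time test.

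- **BAI:** baseline, session 5 and session 10 as three responses; group, time and group × time; unstructured covariance; Bonferroni-adjusted group differences in change from baseline at sessions 5 and 10. The last item also settles which comparisons the Bonferroni adjustment covers. With baseline kept as a response, the three-point test is preserved and participants with only a baseline score stay in the model.
- **POMS:** the ten session scores as responses; group, session and group × session; heterogeneous Toeplitz covariance. State in advance a fallback that allows a persistent between-participant component: a random participant intercept plus AR(1) residuals, or ARMA(1,1). Do not fall back to AR(1) alone.

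The cost is a wording change, with the same data and software. The model assumes scores are missing at random given those observed, and a covariance structure must be fixed before the data are seen.

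### The POMS analysis leaves out baseline BAI, a pre-treatment anxiety score held on everyone; adding it would cost one degree of freedom and could sharpen the between-arm (Group) effect

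*Protocol*

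**What the plan says.** Protocol Section 9 (Statistical Analysis Plan) gives the POMS model in one line: "Secondary outcomes (POMS): Repeated measures ANOVA (Group × Time"). The factors are Group and Time, and no covariate is listed.

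Section 6 (Outcome Measures) lists the "Tension-Anxiety Subscale of the Profile of Mood States (POMS – reduced version") as a secondary outcome, with "Time points: after each of the 10 sessions". No POMS is scheduled before session 1. For BAI, the primary outcome, the same section gives "Time points: baseline, after session 5, after session 10".

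Section 4 (Eligibility Criteria) requires a BAI of at least 11, glossed as "mild anxiety or higher", so a pre-treatment BAI must exist for everyone who enters. Section 7 says "Participants will be randomized into intervention or sham groups using a computer-generated randomization list" and mentions no stratification by baseline anxiety.

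**The concern.** All ten POMS scores follow treatment, so the model contains no pre-treatment information. The part of the between-participant spread in POMS that starting anxiety could explain therefore stays in the error term of the arm comparison. The protocol already collects a pre-treatment score on a related construct and leaves it out of this model.

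The Group effect is the one affected, and it matters for this outcome. Because the first POMS score already follows a session, a benefit present from session 1 and roughly steady afterwards would appear as a difference in level (Group), not as a diverging course (Group × Time). At stake is the precision of that level comparison in a trial whose protocol states no sample size, so spare power cannot be taken for granted.

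**Working it through.** The plan states no sample size, power, effect size, SD or BAI–POMS correlation, so there is no figure to reproduce. The check asks how much the covariate could give over a range of assumptions.

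**Inputs from the protocol.** Ten post-session POMS scores (Section 6); two arms (Section 3); significance level 0.05 (Section 9), taken as two-sided because the side is not stated.

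**Assumed inputs.** 30 per arm; correlation 0.6 between any two POMS scores; correlation r between baseline BAI and each POMS score, the same at every session; true arm difference of 0.5 SD of a single score at every session.

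**Step 1: variance of a participant's 10-session mean**, in units of single-score variance: 0.6 + 0.4/10 = 0.64, so its SD is 0.8. The assumed difference is therefore 0.5/0.8 = 0.625 SD of the session mean.

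**Step 2: unadjusted comparison.** SE = 0.8 × √(2/30) = 0.207. Noncentral t power with 58 df is 66%.

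**Step 3: share of variance removed by baseline BAI.** The correlation with the session mean is r/0.8, so the share is r²/0.64. The adjusted SE is 0.207 × √(1 − r²/0.64), with 57 df:

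| r (single score) | r/0.8 (session mean) | Variance removed | Adjusted SE | Power |
|---|---|---|---|---|
| 0.1 | 0.125 | 2% | 0.205 | 67% |
| 0.2 | 0.25 | 6% | 0.200 | 69% |
| 0.3 | 0.375 | 14% | 0.191 | 73% |
| 0.4 | 0.50 | 25% | 0.179 | 78% |
| 0.5 | 0.625 | 39% | 0.161 | 86% |
| 0.6 | 0.75 | 56% | 0.137 | 95% |

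A simulation of 3,000 runs under the same assumptions gave 73%, 78%, 86% and 95% for r = 0.3 to 0.6, with 4.5% to 5.4% rejection under no effect.

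**Step 4: chance imbalance.** With 30 per arm, the SD of the chance difference in baseline BAI is √(2/30) = 0.258 SD. It reaches the unadjusted POMS difference multiplied by r; at r = 0.5 that is 0.129 single-score SD. This is already inside the unadjusted SE: 0.129² + 0.161² = 0.0166 + 0.0259 = 0.0425, and √0.0425 ≈ 0.206, which is the 0.207 of Step 2 up to rounding. Imbalance and lost precision are thus one quantity seen two ways.

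**Step 5: which effect benefits.** A second simulation (30 per arm, ten sessions, no treatment effect, 4,000 runs, baseline effect constant over sessions) regressed each estimate on the chance baseline difference. Here the correlation is with the participant's underlying POMS level. At correlations 0.3, 0.5 and 0.7, the unadjusted Group effect moved by 0.295, 0.485 and 0.700 SD of that level per 1 SD of imbalance, and by about 0 after adjustment. The linear Group × Time contrast did not respond (about −0.001), and its SD was about 0.023 with or without the covariate. The mean unadjusted Group effect was about 0 (−0.006 to 0.002), so there is no bias.

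**The case against.** The strongest reply is that nothing here is wrong. An unadjusted analysis of a randomised secondary outcome is valid, Section 9 contradicts no other section, and a separate SAP that is not shown might name covariates. This stands as far as validity goes. It is weaker on the last point, because Section 9 carries the title of an analysis plan and states the model itself.

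Second, the POMS line names Group × Time, and that test gains nothing when the covariate slope is constant. This also stands. The same ANOVA does yield a Group effect, but Section 9 does not single it out, so asking for a session-averaged arm difference adds a reported result as well as a covariate.

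Third, the gain rests wholly on assumptions. No document supports a value of r, and the entry threshold on BAI restricts range and may lower it. The gains at r = 0.5 and 0.6 need correlations of 0.625 and 0.75 with the mean of ten post-session scores on a different instrument. At r = 0.1 or 0.2 almost nothing is gained. That is why the range starts at 0.1.

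Fourth, the deeper weakness is that there is no POMS before session 1, for which baseline BAI is only a partial substitute. That is true, but a pre-session POMS means an added assessment, whereas the BAI is already collected.

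A reader might also infer that chance differences in starting anxiety pass in full into the POMS comparison, or distort it beyond what its confidence interval covers. The protocol does not support that. The imbalance enters only in proportion to the BAI–POMS correlation, averages to zero over randomisations, and is part of the unadjusted standard error.

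**Conclusion.** The point holds as an efficiency suggestion. The stated POMS model omits a pre-treatment score held on every participant, and the Group effect loses whatever precision that score could supply. The planned analysis remains valid and unbiased, and the interaction test is unaffected under a constant covariate slope.

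The size cannot be fixed from the protocol. With 30 per arm, inter-session correlation 0.6 and a difference of 0.5 single-score SD, the gain runs from negligible (one to three percentage points of power at r = 0.1 to 0.2) to large (20 and 29 points at r = 0.5 and 0.6). Other sample sizes, or a correlation that fades over the roughly five weeks of treatment, would change these figures. Since POMS is secondary and the cost is close to nil, this is a free improvement and not a defect that threatens the trial's conclusions.

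**What to change.** In Section 9, replace the POMS line with wording such as: *Repeated measures model with Group, Time, Group × Time and baseline BAI as a continuous covariate; the baseline-adjusted between-arm difference in POMS Tension-Anxiety, averaged over sessions, is reported with its 95% CI alongside the Group × Time test.*

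The change should be made before any outcome data are seen, so that the covariate cannot look like a choice made after the results. It costs one degree of freedom, one covariate in the same SPSS procedure and one additional reported estimate. It needs no new data, visits or participants.
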